### **7.10.12.3 1-year Relapse Free Survival (1-yr RFS)**

1-year RFS is defined as the proportion of patients who do not fulfill any of the relapse definitions in section 7.10.11.2 one year after study registration.

### **7.10.12.4 Complete Response (CR)**

Complete response (CR) is defined as disappearance of all bladder tumors (of any T-stage), both grossly and microscopically on urine cytology and post-treatment bladder biopsy.

### **7.10.12.5 Partial Response (PR)**

A partial response (PR) is defined as persistently present, but reduced bladder tumor T-stage on post-treatment bladder biopsy/TURBT in the absence of any new bladder tumors of any stage and in the absence of progression to muscle-invasive stage (i.e.  $\geq T2$ ) of any previously documented bladder tumors. A reduction in the number of bladder tumors but that retains the baseline T-stage does not qualify as a partial response. The following is a list of partial response examples:

T1 → Ta

T1 + Tis → T1

T1 + Tis → Ta

Tis → Ta

### **7.10.12.6 Progression to Muscle-Invasive Disease**

Progression to Muscle-Invasive disease is defined as the appearance of any tumor of  $\geq T2$  at any time in follow-up.

### **7.10.12.7 Progressive Disease (PD)**

Progressive Disease (PD) is defined as the appearance of any muscle-invasive ( $\geq T2$ ) tumor, lymph node metastases (N1-3), or any metastases (M1) at any time in follow-up.

### **7.10.12.8 Best Overall Response**

The best overall response is the best response recorded from the start of the treatment until disease progression/recurrence or non-protocol therapy is documented.

### **7.10.12.9 Duration of Overall Response**

The duration of overall response is measured from the time measurement criteria are met for CR or PR (whichever is first recorded) until the first date that relapsed or progressive disease is objectively documented.

### **7.10.12.10 Duration of Complete Response**

The duration of CR is measured from the time measurement criteria are first met for CR until the first date that relapsed or progressive disease is objectively documented.

### **7.10.13 Safety and Tolerability**

Safety will be monitored by assessing the adverse events at every visit. For details on AE collection and reporting, refer to [Section 8](#).

## **8 Safety Monitoring and Reporting**

### **8.1 Adverse Events**

#### **8.1.1 Definitions and Reporting**

An adverse event for the purposes of this protocol is defined as the appearance of (or worsening of any pre-existing) undesirable sign(s), symptom(s), or medical condition(s).

Abnormal laboratory values or test results constitute adverse events only if they induce clinical signs or symptoms, are considered clinically significant, or require therapy.

Adverse events will be assessed according to the Common Terminology Criteria for Adverse Events (CTCAE) version 4.0. If CTCAE grading does not exist for an adverse event, the severity of mild, moderate, severe, and life-threatening, or grades 1 - 4, will be used. CTCAE grade 5 (death) will not be used in this study; rather, this information will be collected and recorded in the Adverse Events eCRF as end of treatment or survival information.

Adverse events will be recorded from the time of consent and for at least 30 days after treatment discontinuation. All Adverse events considered related to trial medication will be followed until resolution, return to baseline, or deemed clinically insignificant, even if this occurs post-trial.

Abnormal laboratory values or test results occurring after signing the informed consent form constitute adverse events only if they induce clinical signs or symptoms, or require therapy, (e.g., any hematologic abnormality that requires transfusion or hematological stem cell support) or changes in study medication(s) are considered clinically significant and should be recorded on the Adverse Events eCRF under the signs, symptoms or diagnosis associated with them. In addition, isolated abnormal laboratory values that are considered clinically significant (e.g., cause study discontinuation or constitutes in and of itself a Serious Adverse Event) should be recorded on the Adverse Events eCRF.

The occurrence of adverse events should be sought by non-directive questioning of the patient (subject) during the screening process after signing informed consent and at each visit during the study. Adverse events also may be detected when they are volunteered by the patient (subject) during the screening process or between visits, or through physical examination, laboratory test, or other assessments. As far as possible, each adverse event should be evaluated to determine:

1. The severity grade (CTCAE grade 1-4)
2. Causality to the adverse event (reasonable possibility that AE is related to dovitinib): (no, yes)
3. Its duration (start and end dates or if continuing at final exam)
4. Action taken with respect to study or investigational treatment (none, dose adjusted, temporarily interrupted, permanently discontinued, unknown, not applicable)

5. Outcome (not recovered/not resolved, recovered/resolved, recovering/resolving, recovered/resolved with sequelae, fatal, unknown)
6. Whether it is serious, where a serious adverse event (SAE) is defined as in Section 8.2.

**Unlike routine safety assessments, SAEs are monitored continuously and have special reporting requirements, see [Section 8.2](#).**

All adverse events should be treated appropriately. Treatment may include one or more of the following: no action taken (i.e. further observation only); study drug dosage adjusted/temporarily interrupted; study drug permanently discontinued due to this adverse event; concomitant medication given; non-drug therapy given; patient hospitalized/patient's hospitalization prolonged. The action taken to treat the adverse event should be recorded on the Adverse Event eCRF.

Once an adverse event is detected, it should be followed until its resolution or until it is judged to be permanent, and assessment should be made at each visit (or more frequently, if necessary) of any changes in severity, the suspected relationship to the study drug, the interventions required to treat it, and the outcome.

Disease progression should not be regarded or reported as an adverse event itself unless associated with a separate adverse event.

Whenever possible, a diagnosis should be reported instead of underlying signs and symptoms.

### **8.1.2 IND Safety Reports Unrelated to This Trial**

IND safety reports not occurring on this trial but involving the study intervention (outside SAEs) received from outside sources will be reviewed by the Sponsor Investigator and will be forwarded to participating sites for submission to their Institutional Review Boards per their guidelines.

### **8.1.3 Laboratory Test Abnormalities**

#### **8.1.3.1 Definitions and Reporting**

Abnormal laboratory values or test results that constitute adverse events or underlying conditions should not be reported separately in addition to the respective adverse events or underlying diagnosis.

Additionally, laboratory abnormalities that are considered clinically significant due to induction of clinical signs or symptoms, or requiring concomitant therapy (e.g. any hematologic abnormality that requires transfusion or cytokine treatment) or changes in study medication(s), should be recorded on the Adverse Events eCRF. Whenever possible, a diagnosis, rather than a symptom should be provided (e.g. anemia instead of low hemoglobin). Laboratory abnormalities that meet the criteria for adverse events should be followed until they have returned to normal or an adequate explanation of the abnormality is found.

Laboratory abnormalities, that do not meet the criteria of clinical significance, as judged by the investigator, should not be reported as adverse events. A grade 3 or 4 event (severe) as per CTCAE does not automatically indicate a SAE unless it meets the definition of serious as defined below and/or as per investigator's discretion. A dose hold or medication for the lab abnormality

may be required by the protocol in [Section 6](#) and should not contribute to designation of a lab parameter abnormality as a SAE:

## 8.2 Serious Adverse Events

### 8.2.1 Definitions

Serious adverse event (SAE) is defined as one of the following:

- Is fatal or life-threatening
- Results in persistent or significant disability/incapacity
- Constitutes a congenital anomaly/birth defect
- Requires inpatient hospitalization or prolongation of existing hospitalization, unless hospitalization is for:
  - Routine treatment or monitoring of the studied indication, not associated with any deterioration in condition (specify what this includes)
  - Elective or pre-planned treatment for a pre-existing condition that is unrelated to the indication under study and has not worsened since signing the informed consent
  - Treatment on an emergency outpatient basis for an event not fulfilling any of the definitions of a SAE given above and not resulting in hospital admission
  - Social reasons and respite care in the absence of any deterioration in the patient's general condition
  - Any SAEs that are expected due to the condition being treated, including if the SAE is a primary outcome measure, and whether there has been a clear agreement with regulators not to consider these as SAEs, provided the information is collected elsewhere
  - Is medically significant, i.e., defined as an event that jeopardizes the patient or may require medical or surgical intervention to prevent one of the outcomes listed above. Examples of such events include, but are not limited to, intensive treatment in an emergency room or at home for allergic bronchospasm; blood dyscrasias or convulsions not resulting in hospitalization; or the development of drug dependency or drug abuse.

### 8.2.2 Reporting

To ensure patient safety, report every SAE, **regardless of suspected causality**, occurring

- after the patient begins taking study drug and until at least 30 days after the patient has stopped study treatment

Any SAEs experienced after this 30 days period should only be reported if the investigator suspects a causal relationship to the study drug. Recurrent episodes, complications, or progression of the initial SAE must be reported as follow-up to the original episode within 24 hours of the investigator receiving the follow-up information. An SAE occurring at a different time interval or otherwise considered completely unrelated to a previously reported one should be reported separately as a new event.

Information about all SAEs is collected and recorded on the Serious Adverse Event Report Form. The investigator must assess and record the relationship of each SAE to each specific study drug (if there is more than one study drug), complete the SAE Report Form, and send the completed, signed form to **Hoosier Cancer Research Network (HCRN)** within 1 business day of discovery of the event.

Hoosier Cancer Research Network shall notify Novartis upon learning of the occurrence during the study. Events will be reported to the oncology Novartis Integrated Medical Safety (IMS) department. **All events must be reported, by [contact]), to Novartis Pharmaceuticals DS&E Department within 24 hours of learning of its occurrence along with Novartis SAE Report Fax Coversheet.**

The original copy of the SAE Report Form and the fax confirmation sheet must be kept with the case report form documentation at the study site.

Follow-up information is sent to the same person to whom the original SAE Report Form was sent, using a new SAE Report Form stating that this is a follow-up to the previously reported SAE and giving the date of the original report. Each re-occurrence, complication, or progression of the original event should be reported as a follow-up to that event regardless of when it occurs. The follow-up information should describe whether the event has resolved or continues, if and how it was treated, and whether the patient continued or withdrew from study participation.

If the SAE is not previously documented in the Investigator's Brochure (new occurrence) and is thought to be related to dovitinib, an oncology Novartis Integrated Medical Safety (IMS) department associate may urgently require further information from the investigator for Health Authority reporting. Novartis may need to issue an Investigator Notification (IN), to inform all investigators involved in any study with the same drug that this SAE has been reported. Suspected Unexpected Serious Adverse Reactions (SUSARs) will be collected and reported to the competent authorities and relevant ethics committees in accordance with Directive 2001/20/EC or as per national regulatory requirements in participating countries.

#### **8.2.2.1 Study Center (Site) Requirements for Reporting SAEs**

Investigators and other site personnel must report any SAEs occurring during the course of the study within one business day of discovery of the event. This includes events both related and unrelated to the investigational product.

Related means that there is a reasonable possibility the drug caused the adverse experience.

Unrelated	The Adverse Event is clearly not related to the investigational agent(s)
Unlikely	The Adverse Event is doubtfully related to the investigational agent(s)
Possible	The Adverse Event may be related to the investigational agent(s)
Probable	The Adverse Event is likely related to the investigational agent(s)
Definite	The Adverse Event is clearly related to the investigational agent(s)

**The completed SAE Report Form (see SPM) must be faxed to Hoosier Cancer Research Network within 1 business day of discovery of the event.** The investigator is responsible for informing the IRB and/or the Regulatory Authority of the SAE as per local requirements.

The original copy of the SAE Report and the fax confirmation sheet must be kept within the Trial Master File at the study site.

Follow-up information will be faxed to Hoosier Cancer Research Network, using a new SAE Report Form stating that this is a follow-up to the previously reported SAE and giving the date of the original report. Each re-occurrence, complication, or progression of the original event should be reported as a follow-up to that event regardless of when it occurs. The follow-up information should describe whether the event has resolved or continues, if and how it was treated, and whether the patient continued or withdrew from study participation.

#### **8.2.2.2 Death and Immediately Life-Threatening Events**

Any death and immediately life-threatening event from any cause while a patient is receiving trial treatment on this protocol or up to 30 days after the last dose of trial treatment, or any death and immediately life-threatening event occurring more than 30 days after trial treatment has ended but which is felt to be treatment related must be reported **within one business day of discovery of the event**. All deaths must be reported primarily for the purposes of SAE reporting; however, deaths due unequivocally to progression are not SAEs.

Your local IRB should be notified and its reporting procedure followed. The completed SAE Reporting Form should be faxed to Hoosier Cancer Research Network **within one business day of discovery of the event**.

#### **8.2.2.3 HCRN Requirements for Reporting SAEs**

Hoosier Cancer Research Network will report any possibly related SAE to Novartis **within one business day** of receipt of the SAE Reporting Form and to regulatory authorities (FDA) per federal requirements.

Hoosier Cancer Research Network will fax a MedWatch to Novartis and will provide follow-up information as reasonably requested.

### **8.3 Pregnancies**

To ensure patient safety, each pregnancy in a patient on study drug must be reported to Novartis within 24 hours of learning of its occurrence. The pregnancy should be followed up to determine outcome, including spontaneous or voluntary termination, details of the birth, and the presence or absence of any birth defects, congenital abnormalities, or maternal and/or newborn complications.

Pregnancy should be recorded on a Clinical Study Pregnancy Form (see SPM) and reported to Hoosier Cancer Research Network within one business day of learning of its occurrence. Hoosier

Cancer Research Network will report all pregnancies to the oncology Novartis Integrated Medical Safety (IMS) department. Pregnancy follow-up should be recorded on the same form and should include an assessment of the possible relationship to of any pregnancy outcome. Any SAE experienced during pregnancy must be reported on the SAE Report Form.

Pregnancy outcomes must be collected for the female partners of any males who took study drug in this study. Consent to report information regarding these pregnancy outcomes should be obtained from the mother.

## **8.4 Warnings and Precautions**

No evidence available at the time of the approval of this study protocol indicated that special warnings or precautions were appropriate, other than those noted in the provided Investigator Brochure. Additional safety information collected between IB updates will be communicated in the form of Investigator Notifications. This information will be included in the patient informed consent and should be discussed with the patient during the study as needed.

## **8.5 Data and Safety Monitoring Plan**

As this is a small phase II trial of only 20 enrolled patients, a formal data and safety monitoring committee will not be employed. However, the Hoosier Cancer Research Network data management team provides patient safety oversight for all Hoosier Cancer Research Network trials. Specific data and safety monitoring tasks conducted by Hoosier Cancer Research Network include:

- Review of clinical trials conducted for progress and safety
- Review of all adverse events requiring expedited reporting as defined in the protocol
- Review of reports generated by data quality control review process
- Notification of the Sponsor Investigator and funding company of recommended action
- Notification of sites coordinated by Hoosier Cancer Research Network of adverse events requiring expedited reporting and subsequent committee recommendations for study modifications

In addition, Hoosier Cancer Research Network will compile data summary reports for this trial and submit these reports monthly to the Sponsor Investigator. Hoosier Cancer Research Network will submit data summary reports to a Data Safety Monitoring Committee (DSMC) a minimum of twice per year for review.

# **9 Data Review and Management**

## **9.1 Data Confidentiality**

Information about study patients will be kept confidential and managed according to the requirements of the Health Insurance Portability and Accountability Act (HIPAA). Those regulations require a signed patient authorization informing the patient of the following:

- What protected health information (PHI) will be collected from patients in this study

- Who will have access to that information and why
- Who will use or disclose that information
- The rights of a research patient to revoke their authorization for use of their PHI.

In the event that a patient revokes authorization to collect or use PHI, the investigator, by regulation, retains the ability to use all information collected prior to the revocation of patient authorization. For patients that have revoked authorization to collect or use PHI, attempts should be made to obtain permission to collect at least vital status (i.e. that the patient is alive) at the end of their scheduled study period.

The data collection system for this study uses built-in security features to encrypt all data for transmission in both directions, preventing unauthorized access to confidential participant information. Access to the system will be controlled by a sequence of individually assigned user identification codes and passwords, made available only to authorized personnel who have completed prerequisite training.

## **9.2 Site Monitoring**

All study sites will be monitored by Hoosier Cancer Research Network. This includes on-site visits for prior to first study startup for new Hoosier Cancer Research Network sites and annual on-site visits for existing member sites. Sites will be monitored for accuracy, timeliness, and completeness of data collection. Hoosier Cancer Research Network will review source documents for verification of agreement with data submitted via the data collection system. The investigator/ institution guarantee access to source documents by Hoosier Cancer Research Network or its designee and appropriate regulatory agencies. In addition, adherence to protocols through evaluation of study deviations will be analyzed.

The trial site may also be required to participate in a quality assurance audit by Novartis or its designee as well as inspection by appropriate regulatory agencies.

It is important for the investigator and his/her relevant personnel to be available during the monitoring visits and possible audits and for sufficient time to be devoted to the process.

## **9.3 Data Handling and Record Collection**

### **9.3.1 Case Report Forms**

An electronic case report form (eCRF) is required and must be completed for each included patient. The completed dataset is the sole property of Hoosier Cancer Research Network and should not be made available in any form to third parties, except for authorized representatives of appropriate Health/Regulatory Authorities, without written permission from Hoosier Cancer Research Network.

## **9.4 Database Management and Quality Control**

Data will be entered into the study database by investigator/study coordinator for EDC studies.

For studies using eCRFs, Hoosier Cancer Research Network personnel will review the data entered by investigational staff for completeness and accuracy. Detected discrepancies for which the resolution is obvious/self-evident will be corrected by Hoosier Cancer Research Network

Data Management personnel. Electronic data queries are stating the nature of the problem and requesting clarification will be created for all other discrepancies and missing values and sent to the investigational site via the EDC system. Designated investigator site staff are required to respond promptly to queries and to make any necessary changes to the data.

Medical history/current medical conditions and adverse events will be coded using the Medical dictionary for regulatory activities (MedDRA) terminology.

Samples and/or data will be processed centrally and the results will be sent electronically to Hoosier Cancer Research Network.

At the conclusion of the study, the occurrence of any protocol violations will be determined. After these actions have been completed and the database has been declared to be complete and accurate, it will be locked and made available for data analysis.

## **10 Statistical Methods and Data Analysis**

### **10.1 General Considerations**

Statistical analysis of this study will be the responsibility of the Department of Biostatistics at IUSM. Parameter estimates and relevant summary statistics will be reported for both efficacy and safety outcomes. Continuous variables will be summarized by means, medians, minima, maxima and standard deviations. Categorical variables will be summarized by frequencies and percentages. Missing data are expected to be rare. For patients that start therapy but do not make it to the primary endpoint evaluation, their 6-month status will be treated as not achieving CR. Consequently, our estimate of 6-month CR rate will be conservative. For secondary outcomes, missing data, if any, will not be imputed and complete-case analysis will be adopted. Additional exploratory analysis will be conducted when appropriate. Changes from the analysis plan will not require an amendment to the protocol unless it changes a significant feature in the protocol.

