### 3.2.1 Endpoint for Secondary Objectives

- The 1-year relapse free survival rate is defined as the proportion of patients treated with dovitinib with no evidence of any remaining urothelial carcinoma tumors at 12 months of follow-up.

**NOTE:** Patients with residual non-invasive UC tumors with no component of carcinoma in situ (i.e. Ta, T1) at 3-month cystoscopy and TURBT are not considered relapses and will be permitted to continue on dovitinib therapy. If the subsequent 6-month cystoscopy/TURBT, and urine cytology shows no evidence of any remaining urothelial carcinoma in such patients, they will be considered a complete response. Patients with any component of carcinoma in-situ (CIS) at 3-month cystoscopy/TURBT will be considered relapses and will not continue on dovitinib therapy. Any non-invasive UC tumors (i.e. Ta, T1, Tis) at the 6-month or any subsequent cystoscopy/TURBT is considered relapsed disease. Similarly progression to invasive UC tumors (T2-T4) at any time point is also considered relapsed disease and patients will not continue on dovitinib therapy.

- The rate of progression to muscle-invasive stage for dovitinib is defined as the proportion of patients with clinical or pathologic progression to muscle-invasive stages (i.e. T2-T4) at any time point on study. Pathologic progression is assessed by histological finding at TURBT or cystectomy. Clinical progression is assessed by clinician's physical exam and findings on radiologic imaging as ordered per the treating physician's discretion.
- The 3- and 6-month partial response rates are defined as the proportion of patients treated with persistent but reduced T-stage tumors on post-therapy TURBT (i.e. T1 -> Ta; T1+Tis -> T1).
- Treatment related toxicity rates will be assessed by CTCAE v4.0.

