### **7.9 Follow up Period**

All patients must have safety evaluations for 30 days or 5 half-lives (whichever is longer) after the last dose of study treatment. All patients will be followed for tumor relapse status until tumor relapse is noted or for 12 months beyond last dose of study treatment in patients who stopped dovitinib prior to disease relapse.

Patients lost to follow up should be recorded as such on the eCRF. For patients who are lost to follow-up, the investigator should show "due diligence" by documenting in the source documents steps taken to contact the patient, e.g., dates of telephone calls, registered letters, etc.

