### **10.6.2 Secondary Objectives Statistical Considerations**

All secondary objectives are hypothesis generating in nature. One year RFS muscle-invasive progression, 3- and 6-month PR, and toxicity rates will be presented as rates and corresponding 90% Agresti-Coull CIs.

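### A treated patient with no TURBT counts as a failure for 6-month CR but drops out of the partial response rate, so the two rates can have different denominators

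*Combined protocol and SAP*

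**What the plan says.** Section 10.1, repeated in the synopsis under Statistical Considerations, sets two missing-data rules. For a patient who starts therapy but does not reach the primary evaluation, "their 6-month status will be treated as not achieving CR". For the rest, "For secondary outcomes, missing data, if any, will not be imputed and complete-case analysis will be adopted". The same section states: "Missing data are expected to be rare".

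PR at 3 and 6 months is a secondary endpoint. Section 3.2.1 words it this way: "The 3- and 6-month partial response rates are defined as the proportion of patients treated with persistent but reduced T-stage tumors on post-therapy TURBT". Section 10.6.2 gives the analysis: "3- and 6-month PR, and toxicity rates will be presented as rates and corresponding 90% Agresti-Coull CIs". It names no denominator or analysis set. The Efficacy Set in 10.2.5 (at least one dose and one post-treatment evaluation) is not assigned to any analysis.

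The sections that decide who has a TURBT pull in different directions:
- Section 3.2.1: "Patients with any component of carcinoma in-situ (CIS) at 3-month cystoscopy/TURBT will be considered relapses and will not continue on dovitinib therapy". Progression to T2 or above is handled likewise.
- Section 7.9: "All patients will be followed for tumor relapse status until tumor relapse is noted", or for 12 months after the last dose in patients who stopped before relapse.
- Section 7.7.2 takes a patient with a dose delay of more than 14 days off the study and mentions only toxicity follow-up from then on.
- Section 7.10.7.1 schedules the 3- and 6-month TURBT for every patient, and 7.7 asks patients who stop drug to return for the calendar tumor assessments.

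**The concern.** CR and PR at 6 months are read from the same TURBT. Under 10.1 a treated patient without it is a non-responder for one rate and absent from the other. The plan defends its CR rule as conservative and then takes the opposite approach for PR.

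The patients likely to lack a 6-month TURBT are not a random subset. By the plan's own rules they include 3-month relapses, whose relapse follow-up may already have ended, and patients taken off for toxicity. If they are mostly non-PR, removing them raises the PR rate. CR and PR percentages from one visit also could not be added or compared, because they would rest on different numbers of patients.

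**Working it through.** **Inputs.** N = 20 treated patients (10.8), ignoring replacements under 7.8. The two rules come from 10.1 and the 90% Agresti-Coull interval from 10.6.2. The documents give no expected PR rate and no missing-data rate. The number of observed PRs, x = 4, and the number without a 6-month TURBT, m, are therefore assumptions.

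**Interval formula.** With z = 1.645, ñ = n + z², p̃ = (x + z²/2)/ñ, and limits p̃ ± z√(p̃(1−p̃)/ñ). The plan has no PR figure to reproduce, but 10.9 gives Agresti-Coull lower bounds for 4, 5 and 6 of 10 as 0.19, 0.27 and 0.35. The formula returns 0.193, 0.269 and 0.351, so it matches the plan's usage.

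**Inflation if every dropped patient is non-PR.** Complete-case rate = x/(20−m); all-treated rate = x/20; ratio = 20/(20−m), whatever x > 0 is.

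| m | Complete-case PR (90% CI) | All-treated PR (90% CI) | Ratio |
|---|---|---|---|
| 0 | 4/20 = 20.0% (8.9–38.2) | 4/20 = 20.0% (8.9–38.2) | 1.00 |
| 1 | 4/19 = 21.1% (9.4–39.9) | 20.0% | 1.05 |
| 2 | 4/18 = 22.2% (10.0–41.7) | 20.0% | 1.11 |
| 4 | 4/16 = 25.0% (11.4–45.8) | 20.0% | 1.25 |

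**Effect on reading CR and PR together.** Assume 5 CRs, 4 PRs and m = 4. The plan reports CR 5/20 = 25.0% and PR 4/16 = 25.0%, which a reader would add to 50.0%. On one denominator the total is 9/20 = 45.0%.

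**If some dropped patients would have been PR.** Let k of the m be PR. The true rate is (4+k)/20. With m = 4 and k = 1 it is 5/20 = 25.0%, equal to the complete-case figure, so there is no inflation. With m = 2 and k = 1 it is again 25.0%, above the complete-case 22.2%. The upward bias therefore depends on PR being rarer among the dropped patients than among those assessed.

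**Month 3.** CIS or T2+ at month 3 is found at the month-3 TURBT, so those patients are not missing then. Only earlier withdrawals are, and 7.8 replaces them. The problem is mainly at month 6.

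**The case against.** The best defence is that complete-case analysis acts only on missing data, and the plan intends little of it. Section 7.10.7.1 schedules the TURBT for all patients, 7.7 keeps patients who stop drug in the assessment schedule, and 10.1 expects missing data to be rare. PR is hypothesis-generating, drives no decision, and no planned analysis adds it to CR. With two missing, the shift from 20.0% to 22.2% is small beside an interval of 8.9% to 38.2%. The PR wording in 3.2.1 is also not a clean denominator: unlike the CR definition it does not say treated with dovitinib, and the phrase can be parsed in another way.

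Most of this stands as a limit on size. It does not settle the rule. Section 7.7 also says that a patient who stops drug is considered withdrawn after the final visit, and 7.7.2 and 7.9 point towards no further tumor assessment. If every TURBT is done, the change costs nothing.

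Three stronger readings are tempting and are not supported:
- A reader might infer that the plan drops known failures. No section says that a 3-month relapse is missing at 6 months; it could equally be counted as a documented non-PR.
- A reader might infer that no dropped patient is a responder. A patient with residual Ta at 3 months who stops for toxicity has unknown 6-month status, and 3.2 lists T1+Tis to Tis as a PR although CIS at 3 months is a relapse.
- A reader might infer a large bias, for example 3/13 = 23.1% against 3/20 = 15.0%, a ratio of 1.54. That needs 7 of 20 missing, against the plan's expectation. If five of the seven are 3-month relapses that are in fact counted as non-PR, two remain missing: 3/18 = 16.7%, a ratio of 1.11.

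**Conclusion.** The two rules in 10.1 give CR and PR different denominators as soon as one treated patient lacks the TURBT. The plan does not say how a relapse before 6 months is counted for PR. If the dropped patients are non-PR and at least one PR is observed, the PR rate is inflated by 20/(20−m), that is 5% to 25% in relative terms for one to four missing. The direction is likely rather than certain, and the size cannot be taken from the documents. The effect is confined to a descriptive secondary endpoint, mainly at 6 months, and the primary CR analysis is untouched. It is worth correcting because the correction is one sentence.

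**What to change.** In 10.1, 10.6.2 and the synopsis:
- Use the same all-treated denominator for PR as for CR, and state whether patients replaced under 7.8 remain in both.
- Count a patient without the 3- or 6-month TURBT as not PR at that visit, including one with relapse, progression, cystectomy or death before it.
- Keep the complete-case PR rate as a sensitivity analysis, with the number missing and the reasons.

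The PR examples must also be reconciled. T1+Tis to Tis stands in 3.2 and 10.6.1, while T1+Tis to T1 stands in 3.2.1 and 7.10.12.5, and the first conflicts with the 3-month CIS relapse rule. Section 3.2.1 also makes any residual tumor at 6 months a relapse, so the plan should say how a 6-month PR is read beside that.

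Reporting 3-month CR, and CR plus PR at both visits, on this denominator is optional. It would help because PR falls when partial responses become complete.

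The cost is one sentence in each place and no new data. The PR rate becomes slightly lower, and some patients with unknown status are counted as non-PR.
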